Because ASP015K is an immunosuppressive agent, it may increase the risk of infections and reactivation of latent, chronic infections. In particular, excessive immunosuppression can lead to serious infections. Of note is the fact that Xeljanz[®] (tofacitinib) 5 mg, a member of the class of JAK inhibitors to which ASP015K belongs, has been associated with new onset or aggravation of serious infections such as tuberculosis, pneumonitis, sepsis, viral infections, and opportunistic infectious diseases including fungal infections. In addition, several cases of malignant tumors have been reported, although their causal relation to the agent has not been established. Based on the data pooled from 5 domestic and overseas comparative studies of Xeljanz[®] (tofacitinib) 5 mg, the incidence density of malignancies (excluding non-melanoma skin cancers) among RA patients treated with 5 mg BID for a maximum of 1 year was 0.55/100 person-years (incidence rate 0.5% < 5/1216) [Xeljanz[®] Pharmaceutical Interview Form (in Japanese)].

These findings suggest that investigators pay particular attention to the possible development of infections and malignancies and take appropriate measures. Three cases of malignancies (stomach cancer, uterine sarcoma, chronic myelogenous leukemia) have been reported as of the cut-off date of 5 December 2013, from completed and ongoing national and international studies of ASP015K. Only the case of uterine sarcoma was judged as related to ASP015K.

In the Japanese clinical trial in patients with moderate to severe RA (015K-CL-RAJ1), 50 mg and higher doses of ASP015K significantly improved the ACR20 response rate versus placebo. Xeljanz[®] (tofacitinib) 5 mg, which acts via the same mechanism as ASP015K, was approved by the US FDA in 2012 for the treatment of adult patients with moderate to severe RA who had an inadequate response to or are intolerant of MTX. In March 2013, Xeljanz[®] (tofacitinib) 5 mg tablets was authorized for marketing in Japan for treating RA patients who had an inadequate response to conventional therapies. Therefore, a potential benefit of JAK inhibitor ASP015K is to improve RA.

One can also expect that long-term use of ASP015K will improve QOL of RA patients by successfully controlling the RA disease activity over an extended period.

- CONFIDENTIAL -

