The target sample size for the reference group was set at 200 subjects, considering the followings:

- Incidence rates for serious infections from post marketing studies for approved biologic drugs: approximately 1.0% to 3.6% reported in post-marketing all-case surveillance [ACTEMRA[®], drip infusion, 80 mg, 200 mg, 400 mg, final reports for all patients] [ORENCIA[®], drip infusion, 250 mg, information for appropriate drug usage] [HYUMIRA[®], sc, 40 mg, Syringe 0.8 mL, information for appropriate drug usage]; and approximately 2.4% in the 5 mg group and approximately 1.5% in the Adalimumab group, as revealed by pooled analysis of the phase III tofacitinib study [XELJANZ[®], tablet, 5 mg, CTD (2013)]
- Operational feasibility

Setting the sample size of reference group as 200, it can be detectable at least 1 subject with 95% confidence probability for AE which occurs at 1.5% incidence rate.

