- 100 mg: subjects who initially treated as ASP015K 100 mg Group
 - 150 mg: subjects who initially treated as ASP015K 150 mg Group
 - Placebo to 100 mg at Week 12: subjects who initially treated as Placebo group and switched ASP015K 100 mg at Week 12 and at least one dose of ASP015K 100 mg drug after switched
 - Placebo to 150 mg at Week 12: subjects who initially treated as Placebo group and switched ASP015K 150 mg at Week 12 and at least one dose of ASP015K 150 mg drug after switched
 - Etanercept: subjects who initially treated as Etanercept Group
- MedDRA11.1 will be used as the coding dictionary for adverse event and medical history.

- Statistical hypothesis testing will be performed only if specified. All statistical comparisons of treatment groups will be versus placebo (i.e., each ASP015K treatment versus placebo) and will be made using two sided tests at the 0.05 significance level, unless stated otherwise. Multiplicity adjustment will be done in the primary analysis and other analysis if specified.
- Statistical analysis including hypothesis testing for efficacy variables to compare ASP015K 100 mg or ASP015K 150 mg versus Placebo, only the data for the pairwise comparison will be used.
- All statistical results will be presented, as appropriate, by treatment group, by treatment group and scheduled visit; the schedule of assessments is provided in Section 7.11.5-7.
- Demographics and other baseline characteristics will be provided for all ASP015K treatment groups combined ("100 mg + 150 mg") and for all treatment groups, including placebo and reference group, combined ("Total"). Efficacy presentations will not contain combined treatment groups. In study drug exposure, pharmacodynamics and safety presentations, "Total except for Etanercept" will be used in place of "Total".
- Chi-square test is continuity corrected in all analysis.
- Confidence interval for binary outcome is continuity corrected in all analysis.
- Baseline for safety is defined as last non-missing value before the first dose of study drug or reference drug for all subjects including placebo or reference group assigned subjects.
- The values below the lower limit of quantitation (BQL) for β -D-glucan, hCG, Troponin, CK-MB will be treated as it is and these variables are not used for descriptive statistics and displayed in the listings. As for β -D-glucan, it is used for shift-from baseline analysis.

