7.5.1.2 Adverse Events Per 100 Patient-Years

In order to adjust for differences in subjects' durations in the study and the potential differential dropout rates between the treatment groups, TEAEs per 100 patient-years (PYs) will be calculated for each treatment group as follows:

Definition 1:

TEAEs per 100 PYs = $100 \times (\text{Number of subjects who had at least 1 incidence} / \text{Total PYs})$

Total PYs will be calculated by summing individual subjects' durations.

If subjects had at least 1 predefined AE, then the duration of these subjects are summed as from initial dose up to first incidence of predefined AEs.

If subjects had no predefined AE, then the duration of these subjects are summed as from initial dose through follow-up. Summed duration will be divided by 365.25 to represent per year.

Definition 2:

TEAEs per 100 PYs = $100 \times (\text{Number of TEAEs for all subjects in the treatment group} / \text{Total PYs in the treatment group})$.

For number of TEAEs for all subjects in the treatment group, multiple occurrences of the same TEAE in the same subject will be counted multiple times.

Total PYs will be calculated by summing subjects' durations in study through the follow-up period. Each subject's duration will be calculated as: $(\text{last date of follow-up in the study} - \text{date of initial dose of study drug} + 1) / 365.25$.

Patient-Year analysis will be calculated by Placebo, 100 mg, 150 mg, 100mg+150mg, ASP015K Total, Total.

The number of TEAEs and AEs per 100 PYs will be provided by Definition 2, for all TEAEs (if analyzable), by SOC and PT for each treatment group, ASP015K Total and Total.

Patient-Year analysis for following specified AE will also be conducted by Definition 1 with 95% confidence interval.

- Serious Infections
- Malignancies
- Herpes Zoster Related Disease (Herpes Zoster and Varicella)
- Herpes Zoster
- Varicella
- Infections That Require Intravenous Anti-infectious Therapy

Note: Definition will be provided in the Appendix 8.

Confidence Interval for TEAEs per 100 patient-years will be calculated for AE of special Interest based on following formula (assuming Poisson distribution).

- Upper limit of CI log (TEAEs per 100 PYs) : $exp\left(\log\left(\frac{A}{T}\right) + Z_{alpha} * \sqrt{\frac{1}{A}}\right)$
- Lower limit of CI log (TEAEs per 100 PYs) : $exp\left(\log\left(\frac{A}{T}\right) - Z_{alpha} * \sqrt{\frac{1}{A}}\right)$

A: Number of subjects who had at least 1 incidence

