T: Total PYs by 100 PYs as one unit

$Z_{(alpha)}$: alpha % point of standard normal distribution

alpha = 0.025

In addition, the subgroup analysis of Sex, Age Group, Concomitant Steroid at Baseline, and Prednisone Dose at Baseline will be conducted.

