Drug related serious TEAEs leading to permanent discontinuation of study drug or reference drug		X1	
TEAEs excluding serious adverse events that equal to or Exceed a threshold of 5% in Any Treatment Group	X2		
Most common TEAEs (> 5% in any treatment group)	X3	X1	X2
Most common serious TEAEs (> 5% in any treatment group)	X3	X1	X2
TEAEs by subgroups defined in Section 7.8.		X1	
The number and percentage of subjects with TEAEs of special interest	X3	X1	
Serious Infections	X3 ^{#1}	X1 ^{#1}	
Malignancies	X3 ^{#1}	X1 ^{#1}	
Herpes Zoster Related Disease (Herpes Zoster and Varicella)	X3 ^{#1}	X1 ^{#1}	
Herpes Zoster	X3	X1	
Varicella	X3	X1	
Infections That Require Intravenous Anti-infectious Therapy	X3	X1	
Subgroup of TEAEs		X1	
Sex		X1	
Age Group		X1	
Prior Anti-TNF DMARD Use		X1	
Prior Biologic DMARD-IR		X1	
Concomitant DMARD Use at Baseline		X1	
Study Region		X1	
Duration of RA		X1	

Number of Prior DMARDs Used		X1	
Number of Prior Biologic DMARDs Used		X1	
MTX Dose at Baseline		X1	
Concomitant DMARD Category at Baseline		X1	
Protocol Version Number		X1	
Concomitant Steroid at Baseline		X1	
Prednisone Dose at Baseline		X1	
Subgroup of TEAEs of special interest		X1	
Sex		X1	
Age Group		X1	
Concomitant Steroid at Baseline		X1	
Prednisone Dose at Baseline		X1	

X1: Placebo, 100mg, 150mg, Reference

X2: 100mg, 150mg, Placebo to 100 mg at Week 12, Placebo to 150 mg at Week12, Reference

X3: 100mg, 150mg, Reference

#1: Subgroup analysis based on study region or protocol version number will be also presented.

#2: Subgroup analysis based on study region will be also presented.

Table 22. Patient-year analysis

	Week 0 to Week 12	Overall Period
TEAEs (provided by “Definition 2” in 7.5.1.2)	X1	X3
TEAEs of special interest (provided by “Definition 1” in 7.5.1.2)	X1	X3
Serious Infections	X1	X3
Malignancies	X1	X3
Herpes Zoster Related Disease (Herpes Zoster and Varicella)	X1	X3
Herpes Zoster	X1	X3
Varicella	X1	X3
Infections That Require Intravenous Anti-infectious Therapy	X1	X3
Subgroup		X3
Sex		X3
Age Group		X3
Concomitant Steroid at Baseline		X3
Prednisone Dose at Baseline		X3

X1: Placebo, 100mg, 150mg, Reference

X3: 100mg, 150mg, Reference

10.4 Appendix 4: Overview of Clinical Laboratory Evaluation, Vital Signs, and Electrocardiograms (ECGs) analyses

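### The planned confidence interval for adverse events of special interest has no value at zero events, a count this trial should expect, and the SAP gives no fallback

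*SAP*

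**What the plan says.** SAP 7.5.1.2 plans rates per 100 patient-years with 95% confidence intervals for six groups of adverse events of special interest: serious infections, malignancies, herpes zoster and varicella combined, each of those two separately, and infections treated intravenously. The interval is introduced with "Confidence Interval for TEAEs per 100 patient-years will be calculated for AE of special Interest based on following formula (assuming Poisson distribution"), and the limits are exp(log(A/T) ± Z·sqrt(1/A)).

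The terms are defined as "A: Number of subjects who had at least 1 incidence" and "T: Total PYs by 100 PYs as one unit", with alpha = 0.025, so Z is 1.96. On person-time: "If subjects had no predefined AE, then the duration of these subjects are summed as from initial dose through follow-up".

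"Table 22. Patient-year analysis" in SAP Appendix 3 applies this to each event group in four arms for Week 0–12 (placebo, 100 mg, 150 mg, reference) and in three arms for the overall period (100 mg, 150 mg, reference). It then adds overall-period subgroups by sex, age, steroid use and prednisone dose.

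The only general interval rule is in SAP 7.1: "Confidence interval for binary outcome is continuity corrected in all analysis".

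**The concern.** The formula is a Wald interval on the log scale. It needs at least one event to exist and several to behave well. These event groups are rare and many of the cells are small, so the specified method fails where the safety tables are most likely to need it.

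When no event is seen, the useful number is the upper limit, because it shows what rate the data still allow. The planned table would leave that blank. A reader could work it out from the count and the person-time, but the output would not show it. With one or two events, the printed lower limit overstates how firmly a near-zero rate has been excluded.

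Protocol 1.4 singles out infections and malignancies for particular attention, so these rows will be read closely.

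**Working it through.** **The plan's own figure.** SAP Section 4 says 200 reference subjects give 95% probability of seeing at least one event of 1.5% incidence. Check: 1 − 0.985^200 = 0.951, which agrees. In a 100-subject arm the same incidence gives P(0) = 0.985^100 = 0.22.

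**The formula at zero.** A = 0 requires log(0) and 1/0. Neither limit exists.

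**Search for a fallback.** The continuity correction in SAP 7.1 covers binary outcomes, not person-time rates. The qualifier about being analyzable in 7.5.1.2 belongs to the Definition 2 table of all TEAEs. SAP 7.11 and Appendices 3 and 8 have no zero-count rule. SAP 7.1 describes the separate table specifications as covering formats.

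**Inputs.**
- Arm sizes: 100, 100, 100 and 200 (SAP Section 4).
- Person-years per 100 subjects, no dropout: 84/365.25 × 100 = 23.0 to Week 12; 365/365.25 × 100 = 99.9 over 52 weeks; 392/365.25 × 100 = 107.3 over 56 weeks, since subjects without the event count through follow-up.
- Malignancy: the tofacitinib 5 mg rate "was 0.55/100 person-years" (Protocol 1.4).
- Serious infection: "approximately 1.0% to 3.6% reported in post-marketing all-case surveillance" (SAP Section 4). No time base is given; I read these as per 100 person-years, which is an assumption.

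**Probability of no event**, P(0) = exp(−rate × PY/100):

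| Event group and rate | Arm size | Week 0–12 | Overall (52–56 weeks) |
|---|---|---|---|
| Malignancy, 0.55 | 100 | exp(−0.126) = 0.881 | exp(−0.550) to exp(−0.590) = 0.577 to 0.554 |
| Malignancy, 0.55 | 200 | exp(−0.253) = 0.776 | exp(−1.10) to exp(−1.18) = 0.333 to 0.307 |
| Serious infection, 1.0 | 100 | 0.795 | 0.368 to 0.342 |
| Serious infection, 3.6 | 100 | 0.437 | 0.027 to 0.021 |

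**Malignancy row, same rate in every arm.**
- At least one empty cell among the three overall-period arms: 1 − (1 − 0.554)² × (1 − 0.307) = 0.862 at 56 weeks; 0.881 at 52 weeks.
- At least one empty cell among the four Week 0–12 arms: 1 − (1 − 0.881)³ × (1 − 0.776) = 0.9996.

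**Formula against exact Poisson limits** (on the count; divide by T for the rate):

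| A | SAP formula | Exact |
|---|---|---|
| 0 | undefined | 0 to 3.689 |
| 1 | 0.141 to 7.099 | 0.025 to 5.572 |
| 2 | 0.500 to 7.997 | 0.242 to 7.225 |
| 7 | 3.34 to 14.68 | 2.81 to 14.42 |

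The SAP's lower limit is 5.6 times the exact one at A = 1 and 2.1 times at A = 2. The tail probability at that limit should be 2.5%. It is P(X ≥ 1 | 0.141) = 13.1% and P(X ≥ 2 | 0.500) = 9.0%. The SAP's upper limit is conservative. By A = 7 the two intervals nearly agree.

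**What the blank cell would have shown.** The exact upper limit at zero events in a 100-subject arm is 3.689/0.230 = 16.0 per 100 PY to Week 12, and 3.689/1.073 = 3.4 to 3.689/0.999 = 3.7 overall.

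**Pooled column.** If the ASP015K Total includes switched placebo subjects (assumption), it holds 214.6 + 100 × 308/365.25 = 299 PY. The malignancy mean is then 1.64 and P(0) = 0.19.

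**The case against.** The strongest reply accepts the failure at A = 0 but says one added line for that case is enough. With 0 to 3.69/T supplied at zero, the SAP formula's two-sided coverage at overall-period means is at or above nominal: 98.2% at 0.55 and 96.9% at 3.6, for example. For safety the upper limit matters most, and there the SAP errs on the cautious side.

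Those coverage figures are right, but they do not rescue the small Week 0–12 cells. At the malignancy mean of 0.126, the patched formula covers only when A = 0, because its lower limit at A = 1 (0.141) already lies above the true mean. Coverage is 88%. The exact interval also covers at A = 1: 0.881 × (1 + 0.126) = 99%.

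Other points stand as limits on reach:
- The documents give no rates for zoster, varicella or intravenously treated infections.
- Zero is unlikely for serious infection overall at the upper end of the quoted range.
- The malignancy rate is for another drug and excludes non-melanoma skin cancer, whereas the term list in SAP Appendix 8 includes squamous cell carcinoma and carcinoma in situ. At twice the rate, P(0) in a 100-subject arm would still be 0.881² = 0.776 to Week 12 and about 0.554² = 0.307 overall.
- The 16.0 bound assumes person-time is cut at Week 12, which 7.5.1.2 does not state. The chance of seeing no event in those 12 weeks does not depend on how the denominator is written.
- The table specifications were not available. They might say how a missing limit is displayed, but they are not described as setting the method.

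**Conclusion.** The concern holds. The interval as written cannot be computed at zero events, the SAP has no alternative, and at the documents' own malignancy rate zero is the most likely count in every Week 0–12 malignancy cell and in the two 100-subject overall-period cells. Dropout would shorten exposure and make empty cells more likely, as would the subgroup splits.

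The probabilities rest on rates borrowed from other drugs, no dropout, and an annual reading of the serious-infection percentages. The algebraic failure rests on none of these. The effect is confined to descriptive safety intervals and fades at higher counts and in pooled columns. The sponsor should correct it, but the efficacy conclusions are not at risk.

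**What to change.** Replace the formula in SAP 7.5.1.2 with exact Poisson limits, keeping A and T as already defined:

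- lower = chi-square(0.025; 2A)/(2T), taken as 0 when A = 0;
- upper = chi-square(0.975; 2A + 2)/(2T).

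This gives every cell of Table 22 with person-time an interval, including subgroup cells. It needs one changed SAP line and a standard software function. The cost is that exact limits are mildly conservative. Fixing the rule in the plan also avoids choosing a method after the empty cells are known and then having to justify the departure in the study report, as SAP Section 1 requires.

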7.5.1.3 Subgroup Analyses

In order to assess whether or not AEs vary across specific patient groups, AE occurrence will be summarized by SOC and PT for the subgroups specified in Section 7.8

7.5.2 Clinical Laboratory Evaluation

All Laboratory Tests

For clinical laboratory parameters (hematology, biochemistry, fasting lipid profile, and urinalysis), raw values at each scheduled visit, change from baseline at each post-baseline visit, shift from baseline and shift from reference range will be summarized using descriptive statistics or frequency tabulations. No statistical hypothesis testing will be performed. For Fasting Lipids Profile, all analysis will be conducted using the measured values which are confirmed under fasting condition. In addition, all Lipid Profile values including non-fasting condition will also be summarized for descriptive statistics.

Clinical laboratory test is conducted at central institution at each region (Japan, Korea, Taiwan) in accordance with each procedure and each reagent for clinical test. The possibility of harmonization among each region was conducted before clinical laboratory test was initiated in Korea and Taiwan. If clinical laboratory evaluation could be harmonized, then these measurement data among each region could be regarded as the same scale. If harmonization was reported to be difficult, then clinical test would be summarized by Study Region (Japan, Korea, Taiwan). However, among clinical laboratory tests not-harmonized, for exploratory analysis, Beta-D-glucan, Glucose, HCO₃, urine pH, urine gravity will be summarized by whole population. Qualitative Urinalysis test will be summarized by Study Region, only (see 7.8.2 Subgroup analysis for Study Region (Japan, Korea, Taiwan)).

- Clinical laboratory tests harmonized
 - All of the hematology test
 - Biochemistry test except for Beta-D-glucan, Glucose, HCO₃
 - All of the fasting lipid profile
 - CRP
 - Clinical laboratory tests not-harmonized
 - Beta-D-glucan, Glucose, HCO₃
 - All of the urinalysis test
- * For Beta-D-glucan, reference range is not validated throughout the study period and it will be displayed in listing only.
- * Pregnancy test, CPK monitoring, Hepatitis test, Hepatitis DNA test are not applicable to harmonization and it will be displayed in listing only.
- For continuous variables, descriptive statistics of raw values at each scheduled visit will be summarized at each time point using SI unit. For the ratio T-Chol to HDL and the ratio LDL to HDL, descriptive statistics will be summarized at each post-baseline visit.
 - For continuous variables, descriptive statistics of change from baseline value will be summarized at each post-baseline visit using SI unit.
 - Shift-from-baseline table: Shift from baseline baseline to highest value up to Week 12 or during entire period, and baseline to lowest value up to Week 12 or during entire period, for all laboratory variables. If the laboratory value of same subject is measured lower from normal range at one visit, and higher from normal range at the other visit, that subject will be counted as both low and high from baseline up to Week 12 or during entire period.

Laboratory Tests for NCI-CTC Toxicity Grading

Laboratory test results for the select laboratory tests will be graded programmatically using the standardized NCI-CTC toxicity grading criteria (Grade 0, 1, 2, 3, 4) specified in the 10.8 Appendix8 for this study. Shift-from-baseline to worst value up to Week 12 or during entire period will be provided. Note: AEs in this study are graded the investigator using NCI-CTAE Grade (1, 2, 3, 4, 5).

Laboratory Tests for Reference Range

Test results for the select laboratory tests in Table 7 will be summarized against the reference range indicated. Number and percentage for the Highest/Lowest values of each subject included in pre-specified reference range for select laboratory up to Week 12 or during entire period will be provided.

Table 7. Select Laboratory Variables and Corresponding Reference Ranges

Select Laboratory Variable	Reference Range	Highest/Lowest
Aspartate Aminotransferase (AST)	$\geq 1 \times \text{ULN}$ to $< 2 \times \text{ULN}$ $\geq 2 \times \text{ULN}$ to $< 3 \times \text{ULN}$ $\geq 3 \times \text{ULN}$	Highest
Alanine Aminotransferase (ALT)	$\geq 1 \times \text{ULN}$ to $< 2 \times \text{ULN}$ $\geq 2 \times \text{ULN}$ to $< 3 \times \text{ULN}$ $\geq 3 \times \text{ULN}$	Highest
Alkaline Phosphatase (ALP)	$> 2 \times \text{ULN}$ to $\leq 3 \times \text{ULN}$ $> 3 \times \text{ULN}$ to $\leq 5 \times \text{ULN}$ $> 5 \times \text{ULN}$	Highest
Total Bilirubin	$> 1.5 \times \text{ULN}$	Highest
Total Bilirubin	$\geq 1 \times \text{ULN}$ to $< 2 \times \text{ULN}$ $\geq 2 \times \text{ULN}$ to $< 3 \times \text{ULN}$ $\geq 3 \times \text{ULN}$	Highest
Low-Density Lipoprotein (LDL)	$> 160 \text{ mg/dL}$	Highest
Low-Density Lipoprotein (LDL)	$< 100 \text{ mg/dL}$ 100 to $< 130 \text{ mg/dL}$ 130 to $< 160 \text{ mg/dL}$ 160 to $< 190 \text{ mg/dL}$ $\geq 190 \text{ mg/dL}$	Highest
Hemoglobin (HGB)	≥ 8.0 to $< 10.0 \text{ g/dL}$ $< 8.0 \text{ g/dL}$	Lowest
Hemoglobin (HGB)	$\geq (\text{Baseline-2})$ to $< (\text{Baseline-1}) \text{ g/dL}$ $< (\text{Baseline-2}) \text{ g/dL}$	Lowest
Hemoglobin (HGB)	
 Mild to Moderate: decrease from baseline ≥ 1 to $\leq 2 \text{ g/dL}$, Severe: decrease from baseline > 2 to $< 3 \text{ g/dL}$ or absolute value > 7 and $< 8 \text{ g/dL}$, Potentially Life Threatening: decrease from baseline ≥ 3 or absolute value $\leq 7 \text{ g/dL}$ 	Lowest
Creatine Phosphokinase (CPK)	> 500 to $\leq 2,000 \text{ U/L}$ $> 2,000 \text{ U/L}$	Highest
Creatine Phosphokinase (CPK)	$> 5 \times \text{Baseline}$	Highest
Creatine Phosphokinase (CPK)	$> 2 \times \text{ULN}$ to $\leq 5 \times \text{ULN}$ $> 5 \times \text{ULN}$ to $\leq 10 \times \text{ULN}$ $> 10 \times \text{ULN}$	Highest

Select Laboratory Variable	Reference Range	Highest/Lowest
Creatinine	> 1.5 × Baseline to ≤ 3.0 × Baseline > 3.0 × Baseline	Highest
Absolute Neutrophil Count (ANC)	≥ 1,500 to < 2,000 / mm ³ ≥ 500 to < 1,500 / mm ³ < 500 / mm ³	Lowest
Lymphocytes	≥ 200 to < 500 /uL < 200 /uL	Lowest
Lymphocytes	≥ 1,500 to < 2,000 / mm ³ ≥ 500 to < 1,500 / mm ³ < 500 / mm ³	Lowest
Platelets	≥ 2 × 10 ⁴ to < 5 × 10 ⁴ /uL < 2 × 10 ⁴ /uL	Lowest
Platelets	> 600,000 /uL	Highest
ULN = Upper Limit Normal Each categories are mutually exclusive.		

